2.1.4. Exploratory Objectives

• To validate the predictive value of three logistic models having as covariables age, sex and CSF WBC count at baseline, and at 6 and/or

12 months, when used as surrogate markers of treatment success at 18 months or for imputation of missing data (final sensitivity analysis).

• To compare the efficacy of fexinidazole to that of melarsoprol, effornithine and NECT using historical data as comparators.

2.2. Study Endpoints 2.2.1. Primary Endpoint – Efficacy

The primary endpoint is the outcome, either success or failure, of treatment assessed at the test-of-cure (TOC) visit, 18 months after the EOT, based on adapted WHO criteria (54).

An interim analysis will be performed after 195 patients have theoretically reached 12 months of follow-up. The criteria below will apply to the interim analysis.

Success at 12 months is defined as:

- Patient cured, i.e.
 - o patient alive,
 - o AND no evidence of trypanosomes in any bodily fluid,
 - o AND CSF WBC ≤ $20/\mu$ L.

OR

- Patient probably cured, i.e.
 - o no parasites in blood or lymph,
 - AND refusal to undergo lumbar puncture, OR whose CSF sample is haemorrhagic but with no trypanosomes,
 - AND whose clinical status is satisfactory, i.e. with no clinical signs or symptoms, OR whose clinical status is unlikely to be related to HAT
 - Patients with no lumbar puncture at 12 months, but having one at 6 months will be considered as successes if the CSF WBC is ≤ 5/µL

Failure at 12 months is defined as:

- Patient relapsed, i.e.
 - o evidence of trypanosomes in any bodily fluid,

OR

- Patient probably relapsed, i.e.
 - Either no evidence of trypanosomes in any bodily fluid,
 - AND CSF WBC > 20/µL,
 - AND whose WBC cannot be explained by a disease other than HAT,

- o Or no evidence of parasites in the blood or lymph,
 - AND refusal to undergo lumbar puncture, OR whose CSF sample is haemorrhagic but with no trypanosomes,
 - AND who, in the opinion of the Investigator, requires rescue treatment because of marked deterioration in his/her clinical status that is unlikely to be related to a disease other than HAT,
- Or patient who refuses lumbar puncture at 12 months and in whom the outcome had already been assessed as unfavourable at an earlier time (see Table 1 – Definitions of Early Efficacy Endpoints; p Error! Bookmark not defined.),
- Or withdrawal from the study due to probable relapse at any time earlier than 12 months (see Table 1 – Definitions of Early Efficacy Endpoints; p Error! Bookmark not defined.),
- Or patient with no lumbar puncture at 12 months and whose CSF WBC at 6 months was > 5/µL,
- o Or patient with no lumbar puncture at 6 months or 12 months,
- Or death, whatever the cause,
- Or lost to follow-up,

Patients living in an area of armed conflict and who, according to those close to him/her and/or inhabitants of the village, fled the area for a safer region and for whom no post-treatment data are available after several attempts to obtain such information, will not be taken into account in the primary efficacy analysis or in the interim analysis, but will be included in the safety analysis.

Success at 18 months is defined as:

- Patient cured, i.e.
 - o patient alive,
 - o AND no evidence of trypanosomes in any bodily fluid,
 - AND CSF WBC $\leq 20/\mu$ L.

OR

- Patient probably cured, i.e.
 - o no parasites in blood or lymph,
 - AND refusal to undergo lumbar puncture, OR whose CSF sample is haemorrhagic but with no trypanosomes,
 - AND whose clinical status is satisfactory, i.e. with no clinical signs or symptoms, OR whose clinical status is unlikely to be related to HAT.

Failure at 18 months is defined as:

- Patient relapsed, i.e.
 - o evidence of trypanosomes in any bodily fluid,

OR

- Patient probably relapsed, i.e.
 - o Either no evidence of trypanosomes in any bodily fluid,
 - AND CSF WBC > 20/µL,
 - AND whose WBC cannot be explained by a disease other than HAT,
 - o Or no evidence of parasites in the blood or lymph,
 - AND refusal to undergo lumbar puncture, OR whose CSF sample is haemorrhagic but with no trypanosomes,
 - AND who, in the opinion of the Investigator, requires rescue treatment because of marked deterioration in his/her clinical status that is unlikely to be related to a disease other than HAT,
 - Or patient who refuses lumbar puncture at 18 months and in whom the outcome had already been assessed as unfavourable at an earlier time (see Table 1 – Definitions of Early Efficacy Endpoints; p Error! Bookmark not defined.),
 - Or withdrawal from the study due to probable relapse at any time earlier than 18 months (see Table 1 – Definitions of Early Efficacy Endpoints; p Error! Bookmark not defined.)
- Or death, whatever the cause,
- Or lost to follow-up,

Patients living in an area of armed conflict and who, according to those close to him/her and/or inhabitants of the village, fled the area for a safer region and for whom no post-treatment data are available after several attempts to obtain such information, will not be taken into account in the primary efficacy analysis or in the interim analysis, but will be included in the safety analysis.

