12 months	12 months ± 4 weeks	n =195	 Patient alive with no evidence of trypanosomes in any bodily fluid and CSF WBC ≤ 20/µL No evidence of trypanosomes in blood or lymph and refusal to undergo lumbar puncture or whose CSF sample is haemorrhagic but with no trypanosomes and whose clinical status is satisfactory, i.e. with no clinical signs or symptoms, or whose clinical status is unlikely to be related to HAT No lumbar puncture at 12 months, but one at 6 months with CSF WBC ≤ 5/µL 	 No evidence of trypanosomes in any bodily fluid and CSF WBC > 20/µL and whose WBC cannot be explained by a disease other than HAT No evidence of trypanosomes in blood or lymph and refusal to undergo lumbar puncture or whose CSF sample is haemorrhagic but with no trypanosomes and intake of rescue treatment Refusal to undergo lumbar puncture at 12 months and outcome assessed as unfavourable at previous visits Withdrawal from study due to probable relapse at a previous visit No lumbar puncture at 12 months, but one at 6 months with CSF WBC > 5/µL No lumbar puncture at 12 or 6 months 	• Evidence of trypanosomes in any bodily fluid

For statistical purposes, an unfavourable outcome is any situation that does not fulfil the criteria for favourable outcome in Table 1.

Late Efficacy Endpoint (24 months)

The same definitions as those for the primary endpoint will be used. The ideal timing of this visit should be 24 months \pm 4 weeks after EOT.

Surrogate Efficacy Endpoint

The surrogate endpoint is the actual or predicted outcome (if the outcome is missing) at 18 months, based on the outcome at the last visit that took place at 6 months or later, and for which data are available.

The actual outcome, i.e. success or failure, is the same as that defined in the primary endpoint.

The predicted outcome at 18 months is obtained based on logistic models using CSF WBC at baseline, 6 months and/or 12 months, age and sex.

Unlike the primary endpoint, the surrogate endpoint is used to estimate the success rate in the final analysis, i.e. sensitivity analysis of the primary analysis.

In the final analysis, the surrogate endpoint may be much more accurate than the primary endpoint if the predictive value is as good as the results obtained in the set of patients used to construct the models (see Section 9.2 Handling of Missing Values and Lost to Follow-up; p 58).

Safety Endpoints

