⁴ Three logistic models were fitted to MSF data: one using the baseline and 6-month CSF WBC counts, as well as the age and sex of the patient (significant explanatory variables); another using 6-month and 12-month CSF WBC counts; and the last one using the CSF WBC count at 12 months, age and sex. The rate of false positives was 3.3% and the rate of false negatives was 3.0% for patients having a WBC count at 6 and 12 months after EOT. These models provide the probability of being cured at 24 months. The outcome is assessed at 24 months instead of 18 months because most patients in the MSF database had a missing CSF WBC count at 18 months. It is assumed that if cure at 24 months can be adequately predicted using the model, the prediction of cure at 18 months should be conservative due to possible relapses between 18 and 24 months.

⁵ This approach assumes that the predicted probability of success is not dependent on whether or not patients are lost to follow-up in the study. This assumption seems realistic since, in most

patients at 18 months or later, in order to establish whether the outcome is a success because the primary analysis is not based on this rule. Cases that do not comply with the protocol but in which the outcome is known at any time after 18 months will be used in the efficacy analyses. The models will be validated in a blinded manner once all randomised patients have reached the 18-month visit after the EOT (primary endpoint).

Analysis	Method of imputation
Primary	Primary method (method similar to Priotto)
1 st sensitivity analysis	Fourth method: surrogate endpoint (predicted or actual outcome)
2 nd sensitivity analysis (treatment completers)	Primary method
3 rd sensitivity analysis (evaluable patients)	Primary method
4 th sensitivity analysis (per protocol population)	Fourth method
5 th sensitivity analysis	Second method (patient lost to follow-up = failure)
Planned secondary analysis (K-M analysis)	Third method

For the interim analysis, if the lumbar puncture is missing at M12:

- if a lumber puncture was performed at M18, the result at M18 will be used,
- o if a lumber puncture was performed at M6, success will be imputed if the WBC count is ≤ 5/µL, no trypanosomes are detected and no symptoms related to HAT are present at 12 months,
- if data for lumbar puncture are available at M6 and at M18, the outcome at M18 will prevail.

All other cases in which the lumbar puncture is missing will be considered as failures.

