This threshold is slightly lower than the historical difference between effornithine and melarsoprol at 12 months, i.e. \approx 15%. It should be noted that, at this stage, the study will be stopped if the result is significantly worse than the margin of an unacceptable difference, whereas the final analysis will be positive if the result is significantly better than the margin of an unacceptable difference.

Interim Analysis for Success

An interim primary analysis for success will be performed on the first 195 randomised patients who have theoretically reached 12 months of follow-up, excluding patients for whom no post-treatment data are available because the patient is known to have fled the area strictly for reasons of armed conflict. The analysis will be identical to the final primary analysis with the exception of the threshold for significance (see Adjustment of Type-I Error for Multiplicity) and the assessment visit, which will be 12 months instead of 18 months.

A sensitivity analysis, including all randomised patients, will be performed and will consider all patients who fled for reasons of armed conflict as failures.

If the interim primary analysis for success should not prove to be significant, no further interim secondary or sensitivity analyses will be performed. If the analysis proves to be significant, all of the interim secondary and sensitivity analyses will be performed in accordance with the approach described for the final analyses, i.e. those initially planned. In addition, the success rate at 18 months will be compared, using a superiority test, to the historical success rate for melarsoprol at 18 months, i.e. 73.7%. No adjustment of the threshold for significance will be made in this analysis. The time course of the success rate, i.e. EOT, 6 months, 12 months and 18 months, will be studied using the Kaplan-Meier approach. The cumulative failure rate at each visit will be presented graphically including historical data for melarsoprol and effornithine.

Adjustment of Type-1 Error for Multiplicity

No adjustment will be made for the FAs, because the study cannot be prematurely discontinued for success based on an FA. In this case, Chen has shown that performing such analyses slightly reduces the final type-I error (9).

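### The 12-month interim endpoint classes a clinically well patient who refuses the lumbar puncture as both success and failure, and the sections that could settle it point in different directions

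*Protocol*

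**What the plan says.** Section 2.2.1 states that its 12-month criteria apply to the interim analysis.

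- **Success list.** One route to probable cure rests on the clause "AND refusal to undergo lumbar puncture, OR whose CSF sample is haemorrhagic but with no trypanosomes". It also asks for negative blood and lymph and for a clinical picture that is good or not attributed to HAT. No month-6 result is required. A further bullet reads "Patients with no lumbar puncture at 12 months, but having one at 6 months will be considered as successes if the CSF WBC is" at or below 5/µL.
- **Failure list.** It includes "Or patient with no lumbar puncture at 12 months and whose CSF WBC at 6 months was > 5/µL", then any patient with no puncture at 6 or 12 months, then death and loss to follow-up. It makes no exception for a well patient who refuses.
- **Table 1, interim row.** It repeats both sides. The refusal route and the month-6 route are separate favourable entries, and "No lumbar puncture at 12 or 6 months" is a probable relapse.
- **General rules around Table 1.** The sentence above it counts every probable relapse and every death as a relapse in all analyses. The note below it defines unfavourable as whatever does not meet the favourable criteria.
- **Section 9.2, interim rule.** A month-18 puncture replaces a missing month-12 one. Failing that, a month-6 count of 5/µL or less is a success if there are no trypanosomes and no HAT symptoms at month 12. Then: "All other cases in which the lumbar puncture is missing will be considered as failures".
- **Section 9.11.** "The analysis will be identical to the final primary analysis with the exception of the threshold for significance" and the visit. The Protocol Summary lists a third exception, the imputation rule.

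**The concern.** An endpoint has to put each patient in one category. Here an identifiable group falls in two, and the month-18 override appears in only one of the places that define the endpoint.

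The interim matters because section 9.11 gives its aim as faster submission of the registration dossier. The disputed patients have no month-12 CSF result and are judged clinically by investigators who know the treatment. The rule for them should be fixed before the independent statistician unblinds.

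**Working it through.** **Step 1. Apply each text to the same patients.** All rows assume no month-12 puncture.

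| Patient | 2.2.1 and Table 1 | 9.2 |
|---|---|---|
| A. Well, blood and lymph negative, refuses; month-6 WBC 6-20; no month-18 puncture | success (refusal route) and failure (>5 bullet) | failure |
| B. As A, but no month-6 puncture | success (refusal route) and failure (no-puncture bullet) | failure |
| C. Month-6 WBC >5; good month-18 puncture | failure (also success if a well refuser) | success |
| D. Month-6 WBC ≤5; month-18 WBC >20 | success | failure |
| E. Lost after month 6; month-6 WBC ≤5 | success (month-6 bullet) and failure (lost) | failure, as freedom from symptoms at month 12 cannot be shown |
| F. Well refuser; month-6 WBC ≤5; no month-18 puncture | success | success |

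In row A, Table 1 treats a month-6 count of 20/µL or less as favourable. The separate failure bullet for refusers with an earlier unfavourable outcome therefore does not remove the overlap. Row F shows that not every missing puncture is in dispute.

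**Step 2. Reproduce the plan's power.** The inputs are 94% NECT, 89% fexinidazole, margin 13%, one-sided 0.025 and 130 + 260 patients (section 9.1).

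Power = Φ[(m − (pN − pF))/SE − z], with SE = √[pN(1−pN)/nN + pF(1−pF)/nF].

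SE = √(0.94×0.06/130 + 0.89×0.11/260) = 0.02847. Then (0.13 − 0.05)/0.02847 − 1.960 = 0.850 and Φ = 80.2%, against the stated 80%.

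**Step 3. Apply the same formula at the interim.** The 195 patients split 2:1 give 65 NECT and 130 fexinidazole. Section 9.11 names Pocock but prints no threshold. For two looks, the first at half the information, z = 2.178 (one-sided 0.0147); this is an assumption.

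The size of the disputed group is also assumed. Counting as failures a share q of otherwise successful patients, equal in both arms, multiplies both rates by (1 − q).

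| q | NECT / fexinidazole | SE | (margin − difference)/SE − 2.178 | Chance of significance |
|---|---|---|---|---|
| 0 | 0.940 / 0.890 | 0.04026 | 0.08/0.04026 − 2.178 = −0.191 | 42.4% |
| 5% | 0.893 / 0.8455 | 0.04975 | 0.0825/0.04975 − 2.178 = −0.520 | 30.2% |
| 10% | 0.846 / 0.801 | 0.05684 | 0.085/0.05684 − 2.178 = −0.683 | 24.7% |

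Exact binomial calculation gives 42.6%, 28.9% and 23.3%. If 5 or 10 percentage points are instead subtracted from each arm, the exact figures are 26.3% and 19.9%. If both true rates are 94%, subtracting 5 points takes the exact chance from 95.4% to 74.0%.

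**Step 4. Sensitivity to one patient.** One reclassified patient moves the rate by 1/130 = 0.77 points (fexinidazole) or 1/65 = 1.54 points (NECT). With NECT at 61/65, fexinidazole at 117/130 gives z = 2.30 and passes; at 116/130 it gives z = 2.08 and fails.

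**The case against.** The strongest reply is that one rule was intended and can be found. The three month-6 bullets, which the 18-month list lacks, divide the patients without a month-12 puncture into at or below 5, above 5, and no month-6 puncture. Apart from the month-18 override, and the month-12 symptom and parasite conditions that section 9.2 adds, they match section 9.2. The sentence above Table 1 also sends probable relapses to failure. On this view the refusal clause is text carried over from the 18-month list.

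That is probably the intention, but it does not settle the matter. The note under Table 1 points the other way for anyone who meets a favourable criterion. Table 1 lists the refusal route as a criterion of its own, so the month-6 bullet cannot safely be read as qualifying it. Nothing says that section 9.2 prevails over the endpoint definition.

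Some stronger readings that a reader might infer are not supported:

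- **A patient who dies after month 6 is also a success.** The month-6 bullet does not mention survival, but section 2.2.1 makes death from any cause a failure and the sentence above Table 1 repeats this. The gap concerns patients lost to follow-up.
- **Section 9.11 makes refusers successes by importing the final rule.** It leaves the imputation rule out of its exceptions, but the Summary includes it. This is an omission to repair, not a competing rule.
- **The haemorrhagic-sample clause conflicts in the same way.** A haemorrhagic sample means that a puncture was done, so it is not clearly missing. Deleting the clause would go beyond the conflict.
- **The sponsor can choose the rule after seeing results.** Data handling and review are blinded and an independent statistician runs the interim test. The ambiguity leaves room for a late choice but does not show that one would be made.

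**Conclusion.** The concern holds for the interim endpoint. It is not uniquely defined for well refusers with a month-6 count above 5/µL or no month-6 puncture, for patients whose month-18 puncture disagrees with the month-6 rule, or for patients lost after a month-6 count of 5/µL or less.

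The size cannot be fixed from the documents. The fall from about 42% to about 30% or 25% rests on an assumed 5% or 10% overlap, equal in both arms, and on the assumed Pocock threshold. It shows a lower chance of success under the stricter rule, not an inflated false-positive rate.

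The consequence is limited to the interim result and what it triggers. The study continues whatever the interim shows. The 18-month failure list has no month-6 or missing-puncture bullets of this kind, so the final analysis is not affected.

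**What to change.** Before interim unblinding, put one ordered, mutually exclusive statistical classification for a missing month-12 puncture in section 2.2.1, Table 1, section 9.2 and section 9.11, consistent with section 9.2:

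1. If a month-18 puncture exists, use its result.
2. Otherwise, month-6 CSF WBC ≤5/µL with no trypanosomes and no HAT symptoms at month 12 is a success.
3. Every other missing puncture is a failure.

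Limit the refusal clause of probable cure to agree with this. State separately how a haemorrhagic, trypanosome-free sample is classed. Keep deaths as failures, and keep the armed-conflict exclusion and the qualifier for a raised count explained by another disease. Add the imputation rule to the exceptions in section 9.11. Run the alternative classification, with well refusers as successes, as a sensitivity analysis.

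This concerns statistical classification only and changes nothing in patient management. The cost is protocol and SAP wording, one extra analysis and a slightly lower interim success rate in both arms.

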2.2.2. Secondary Efficacy Endpoints or Exploratory Endpoints Early Efficacy Endpoints

The early efficacy endpoints used in the futility and secondary analyses vary depending on the timepoint and analysis.

Futility analyses (FAs) assessing the response rate are planned in order to stop exposure to the IP if efficacy is below an acceptable limit (see Section 9.11 Futility Analyses; p 67).

All cases of probable relapse and all deaths will be included as relapses in all analyses.

Table 1 - Definitions of Early Efficacy Endpoints, for statistical purposes only

	Ideal		Responder /	Non-responder / Relapse	
Timepoint	timing of visit after EOT	Analyses	Favourable outcome	Probable Relapse	Confirmed Relapse
24 hours after EOT	Within 2 days	FA1 n ₁ =20 Fexi FA2 n ₂ =70 Fexi	• Patient alive with no evidence of trypanosomes in any bodily fluid (54)		• Evidence of trypanosomes in any bodily fluid
3 months	3 months ± 1 week	FA3 n₃=70 Fexi	 Patient alive with no evidence of trypanosomes in any bodily fluid (no lumbar puncture at 3 months unless Investigator suspects relapse) 	 Neurological signs or symptoms leading to use of rescue treatment 	• Evidence of trypanosomes in any bodily fluid
6 months	6 months ± 2 weeks	FA4 n₄=70 Fexi	 Patient alive with no evidence of trypanosomes in any bodily fluid and CSF WBC ≤ 20/µL 	 CSF WBC ≥ 50/µL (36) Neurological signs or symptoms leading to use of rescue treatment 	• Evidence of trypanosomes in any bodily fluid
			 If uncertain (CSF WBC between 20 and 50/µL), request additional visit in 1-3 months 		
12 months	12 months ± 4 weeks	FA5 n₅=70 Fexi	 Patient alive with no evidence of trypanosomes in any bodily fluid and CSF WBC ≤ 20/µL CSF WBS between 20 and 50/µL, and lower as compared to previous value(s) 	 CSF WBC ≥ 50/µL CSF WBC > 20/µL and higher as compared to previous value(s) Neurological signs or symptoms leading to use of rescue treatment 	• Evidence of trypanosomes in any bodily fluid

Protocol number DNDiFEX004 Version 4.0

DNDi / Fexinidazole

12 months	12	Interim	Patient alive	No evidence of	Evidence of
12 months	12 months ± 4 weeks	n =195	 Patient alive with no evidence of trypanosomes in any bodily fluid and CSF WBC ≤ 20/µL No evidence of trypanosomes in blood or lymph and refusal to undergo lumbar puncture or whose CSF sample is haemorrhagic but with no trypanosomes and whose clinical status is satisfactory, i.e. with no clinical signs or symptoms, or whose clinical status is unlikely to be related to HAT No lumbar puncture at 12 months, but one at 6 months with CSF WBC ≤ 5/µL 	 No evidence of trypanosomes in any bodily fluid and CSF WBC > 20/µL and whose WBC cannot be explained by a disease other than HAT No evidence of trypanosomes in blood or lymph and refusal to undergo lumbar puncture or whose CSF sample is haemorrhagic but with no trypanosomes and intake of rescue treatment Refusal to undergo lumbar puncture at 12 months and outcome assessed as unfavourable at previous visits Withdrawal from study due to probable relapse at a previous visit No lumbar puncture at 12 months, but one at 6 months with CSF WBC > 5/µL No lumbar puncture at 12 or 6 months 	• Evidence of trypanosomes in any bodily fluid

For statistical purposes, an unfavourable outcome is any situation that does not fulfil the criteria for favourable outcome in Table 1.

Late Efficacy Endpoint (24 months)

The same definitions as those for the primary endpoint will be used. The ideal timing of this visit should be 24 months \pm 4 weeks after EOT.

Surrogate Efficacy Endpoint

The surrogate endpoint is the actual or predicted outcome (if the outcome is missing) at 18 months, based on the outcome at the last visit that took place at 6 months or later, and for which data are available.

The actual outcome, i.e. success or failure, is the same as that defined in the primary endpoint.

The predicted outcome at 18 months is obtained based on logistic models using CSF WBC at baseline, 6 months and/or 12 months, age and sex.

Unlike the primary endpoint, the surrogate endpoint is used to estimate the success rate in the final analysis, i.e. sensitivity analysis of the primary analysis.

In the final analysis, the surrogate endpoint may be much more accurate than the primary endpoint if the predictive value is as good as the results obtained in the set of patients used to construct the models (see Section 9.2 Handling of Missing Values and Lost to Follow-up; p 58).

Safety Endpoints

Adverse events will be graded according to the National Cancer Institute (NCI) Common Toxicity Criteria for Adverse Events (CTCAE), Version 4.03.

- Occurrence of adverse events, all grades combined, during the observation period, i.e. from D1 to D8, including:
 - any worsening of the clinical symptoms listed among the signs and symptoms to be checked prior to inclusion,
 - laboratory abnormalities \geq grade 2,
- Occurrence of any adverse events ≥ grade 3 during the observation period,
- Occurrence of any treatment-related adverse events, ≥ grade 3 and all grades combined, during the observation period,
- Occurrence of any serious adverse events between the first treatment intake and the end of the follow-up period (18 months), and between Month 18 and Month 24.

Potentially significant ECG abnormalities will be reported after centralised ECG review.

Pharmacokinetic Endpoints

PK sampling in patients in the fexinidazole group will only be performed at the first 6 investigational sites.

Concentrations of fexinidazole, M1 and M2 in whole blood and in CSF, as well as PK parameters derived from a population PK model.

- Samples of whole blood will be collected using dry blood spot (DBS) testing on a finger-prick sample at the following timepoints:
 - o on Day 8, 3 hours and 15 minutes after intake of the IP,
 - o on Day 9, 3 hours after intake of the IP,
 - $\circ~$ on Day 10, 3 hours and 7 hours and 15 minutes after intake of the IP,
 - o on Day 11, 24 hours after intake of the IP,

- o on Day 12, 48 hours after intake of the IP.
- Lumbar puncture will be performed on Day 11, 24 hours after intake of the IP for the EOT efficacy assessment. A dry CSF spot will be collected at the same time for PK analyses for all patients until the end of July 2013.

ECG Endpoints

Triplicate ECG tracings will be recorded at 2-minute intervals to assess QT interval at the following timepoints:

- At baseline for all patients
- Thereafter:
 - in patients in the fexinidazole group: on Day 4, 4 hours (H4) after intake of the IP, on Day 4 Hour 23, and on Day 10 2-3 hours after intake of the IP,
 - in patients in the NECT group: on Day 7 2-3 hours after treatment intake in the morning and on Day 10 2-3 hours after treatment intake in the morning.

Triplicate ECGs and a safety ECG will be collected for different purposes and will be analysed separately (see Section 6.3.2 ECG Recordings; p 47).

3. Study Design

This is a pivotal, phase-II/III, randomised, open-label, multicentre study with two unbalanced parallel (2:1 ratio) groups, comparing fexinidazole and NECT as the active control.

4. Selection of Study Population

To be eligible for inclusion in the study, patients must fulfil all of the inclusion criteria and none of the exclusion criteria.

